5. RANDOMIZATION

5.1 Overview

Randomization will be used to avoid bias in the assignment of treatment to each subject to increase the likelihood that attributes of the subject are evenly balanced across treatment groups, and to enhance the validity of statistical comparisons across treatment groups.

5.2 Procedures

ETHICON will provide each site with computer-generated randomization envelopes, each bearing the subject randomization number, and containing the treatment allocation. Treatment will be assigned randomly to each subject on a 2:1 basis to either EVICEL® or adjunctive repair sutures only.

In the event that a potential subject fails intraoperative criteria, and is not randomized to the study, the unused randomization envelope should be returned to the series, and used for the next subject.

Given the difference between the two treatment groups, it will not be possible for the surgeon to be blinded to the treatment. However, to avoid any bias in the conduct of the surgical procedure, randomization should only take place after sutured dural closure and the detection of CSF leakage.

6 INVESTIGATIONAL PRODUCT AND CONTROL GROUP

6.1 EVICEL® (Treatment Group)

6.1.1 Formulation

EVICEL® is a human plasma-derived fibrin sealant. EVICEL® consists of two components: a concentrate of Human clottable protein containing mainly fibrinogen (referred to as Biological Component 2; BAC2) and a stabilized solution of Human Thrombin, which incorporates calcium. No material of animal origin is present in the product.

A purpose-designed application device is used to apply EVICEL® to the surgical site by spraying or dripping and has been designed to ensure even mixing of the two components.

Composition of EVICEL®

	Human Fibrinogen	Human Thrombin
Active Ingredient	Concentrate of human clottable protein containing mainly fibrinogen	Human thrombin
Other Ingredients	Arginine hydrochloride, Glycine, Sodium chloride, Sodium citrate, Calcium chloride, Water for injection (WFI)	Calcium chloride, Human albumin, Mannitol, Sodium acetate, Water for injection (WFI).

In this study 2ml kits (1ml vial of Fibrinogen & 1ml vial of thrombin) will be provided to investigators.

6.1.2 Labelling and Packaging

The investigational product will have two vials and a Package Leaflet contained within a single box. The product will be labelled according to local regulatory requirements and may contain the following information:

- Name and address of manufacturer / sponsor
- Protocol number
- Lot/Batch number
- Expiry date
- EudraCT number
- Storage conditions
- Statement that the product is limited for clinical trial use only

6.1.3 Shipping, Handling and Storage Conditions

Distribution of EVICEL® kits to the clinical sites will be performed by a qualified person (QP) or appropriate distribution center with proper inventory and quality control capabilities once all the necessary documentation and approvals are obtained.

The two components of the EVICEL® Kit are frozen, and must be stored at -18°C or colder. EVICEL® will be shipped to each site on dry ice during which the temperature will be monitored continuously. Once at the site, the product will be stored in a freezer at -18°C or colder.

The application devices will be shipped and stored at ambient temperature.

6.1.4 Application Device

The application device is commercially available in the US, Canada and several European countries. It is not considered as an investigational product. Depending on its regulatory status, the product will be labelled according to local regulatory requirements, and may contain the following information:

- Name and address of manufacturer
- Protocol number
- Statement that the product is limited for clinical trial use only

6.1.5 Accessory Tips

The accessory tips are commercially available in the US, Canada and several European countries. They are not considered as an investigational product. Accessory tips provided for use with the application device when the tip commercially available in the appropriate country including:

- Standard yellow tip (provided with application device)
- 4 cm Control Tip
- Airless Spray Accessory

Any tip may be used, according to surgeon preference. Tips will be used in accordance with their Product Assembly Guide and Investigator Brochure.

6.1.6 Pressure Regulators

The pressure regulators may be provided when commercially available. They will be used according to the investigator brochure and are not considered as an investigational product.

6.1.7 Preparation

The two frozen components of EVICEL® (BAC2 and Thrombin) must be thawed before use, using one of the following methods:

- 2-8°C (refrigerator): vials thaw within one day; or
- 20-25°C (room temperature): vials thaw within one hour; or
- 37°C; vials thaw within ten minutes and should not be left at 37°C for more than 10 minutes. The temperature must not exceed 37°C.

Thawed, unopened vials must be stored, at the temperature range stated within the Investigator Brochure. Thawed vials must not be re-frozen. Vials thawed at room temperature or above should be used within 24 hours and not returned to refrigerated storage.

Before use, the product must reach 20-30°C.

After thawing, preparation of the product must occur in a sterile surgical field. The two components should be drawn into the application device, following directions enclosed in the application device package. Both syringes must be filled with equal volumes, and should not contain air bubbles. Selection of the appropriate application tip will be left to the discretion of the surgeon.

6.1.8 Dose, Route and Duration of Administration

For each subject, at least one kit of EVICEL® (BAC2 and Thrombin) will be thawed and available for administration prior to randomization. EVICEL® will be sprayed or dripped onto the tissue to produce a thin, even layer. A cure time of 1-2 minutes should be allotted between applications to allow for polymerisation. The amount of EVICEL® required depends upon the area of tissue to be treated and the method of application.

Application can be made by dripping or spraying in accordance with the EVICEL® Investigator Brochure, Accessory Tip Directions and Device and Pressure Regulator Instructions for Use.

6.2 Investigational Product Dispensation and Accountability

A dispensing log will be kept by the designated study personnel. This log will contain information on the date of administration, subject ID and quantity of EVICEL® dispensed, details of any remaining product, and subsequent destruction. The study monitor will verify these logs during the course of the study.

6.3 Additional Sutures Only (Control Group)

Subjects randomized to control will receive additional dural repair sutures as deemed necessary by the surgeon to attempt to achieve a watertight closure.

6.4 Concomitant Medications

6.4.1 Topical Hemostats

The use of flowables, other fibrin sealants, and topical absorbable hemostats such as SURGICEL® will be permitted for hemostasis of the brain and must be used according to their labelling and the surgeon's usual practice.

6.4.2 Documentation of Concomitant Medications

Indication and start-stop dates of concomitant medications administered from 24 hours prior to surgery up to the follow up contact or evaluation will be recorded.

Anesthetics used for surgery and over the counter (OTC) drugs (except for prophylactic aspirin, which should be documented) will not be recorded as concomitant medication except when used to treat an adverse event.

7 STUDY EVALUATIONS

7.1 Study Procedures

The schedule of events included in the synopsis summarizes the frequency and timing of the study procedures. Data collected for the subject during the study will be recorded in the subject's medical records, and study worksheets or source documents, as appropriate, and recorded into the eCRF.

7.1.1 Screening (Within 21 Days Prior to Surgical Procedure)

Prospective subjects will be screened within 21 days prior to surgery. Prior to any study related procedures, subjects will be fully informed of all aspects of the study. Subjects or subject legal representative/parent will be asked to sign a Consent Form. Assent process will also occur when applicable.

The following tests and procedures will be performed at the screening visit. The timing of when these activities may occur will be based on routine hospital practice; The Screening Visit may be combined with the Baseline visit.

- Informed consent & assent process as applicable.
- Allocation of screening number.
- Documentation of demography (age, gender, race, ethnic origin).
- Physical examination, including documentation of relevant medical and surgical history.
- Review of Inclusion / Exclusion criteria to confirm subject eligibility.

7.1.2 Baseline Assessments (Within 24 Hours Prior to Procedure)

The following activities will be performed within 24 hours prior to the procedure:

- Review of inclusion / exclusion criteria to confirm subject eligibility. In the event that a subject is not eligible, the reason will be documented.
- Laboratory tests: electrolytes, creatinine, full blood count (FBC), liver and function test (LFT).
- Serum or urine pregnancy test (if necessary).
- Document all concomitant medications during 24 hours prior to surgery. (see Section 6.4)
- Document any changes in medical history from the screening visit.

7.1.3 Surgical Procedure

The surgeon will use his/her standard surgical techniques for the surgical procedure. The following activities will be performed, and information will be collected, during the surgical procedure:

- Details of procedure including:
 - Operative Procedure (for example: Craniotomy or Craniectomy)
 - Type of procedure (for example: Posterior fossa or Supratentorial)
 - Length of procedure (from first incision to closure completed); and
 - Time in Operating Room (OR) (time subject entered OR and time subject exited OR).
- Intraoperative confirmation of eligibility
- Primary sutured dural closure (use of a tissue based patch autologous/ non-autologous is permitted)

Randomization Procedures:

- EVICEL® will be prepared and available in the sterile field in the operating room, ready for administration for each subject.
- If the subject is randomized to additional sutures, the unused EVICEL® treatment product **MUST** immediately be removed from the sterile field and placed for destruction. After the procedure, accountability of the product should be documented.
- Upon completion of the primary sutured dural repair, the closure will be evaluated for intraoperative CSF leakage. If a leak is present the subject will be randomized into the study. If a spontaneous leak is not present following primary suture repair the closure will be tested with a baseline Valsalva maneuver 20-25 cm H₂O for 5-10 seconds.
- Subjects who have a CSF leak (spontaneous or upon Valsalva) will be randomized into the study.
- The subject will be randomized immediately upon proper identification of a leak by opening the appropriate randomization envelope.

Treatment application:

- **Subjects Randomized to EVICEL**
For subjects randomized to receive EVICEL® Fibrin Sealant (Human), a thin layer will be applied to the entire length of the suture line and the adjacent area to at least 5mm away, including all suture holes.

If necessary, a second layer of EVICEL® may be applied. A cure time should be allotted between layers to allow for polymerization. CSF leakage will be evaluated with the Valsalva maneuver 20-25 cm H₂O for 5-10 seconds. Application technique, spray or dripping, will be determined by surgeon preference. Method of application will be recorded.

If CSF leakage is still apparent a second treatment (up to two layers) with EVICEL® may be applied. CSF leakage will be re-evaluated with the Valsalva maneuver 20-25 cm H₂O for 5-10 seconds.

If watertight closure is not evident after this second Valsalva maneuver, the subject will be deemed a **failure** and the surgeon may revert to his/her standard of care for closure including the use of other commercially available fibrin sealants (except EVICEL®) or an onlay dural patch.

If watertight closure is achieved with EVICEL®, no additional adjunct should be used and the subject will be deemed a **treatment success**.

Closure of the remaining layers of the surgical site will be performed according to the surgeon's standard of practice.

- **Subjects Randomized to Additional Sutures (Control Group)**

Subjects randomized to control will receive additional dural sutures as deemed necessary by the surgeon. CSF leakage will be evaluated with the Valsalva maneuver 20-25 cm H₂O for 5-10 seconds.

If watertight closure is not evident after the Valsalva maneuver, the subject will be deemed a **failure** and the surgeon may revert to his/her standard of care for closure including the use of other commercially available fibrin sealants (except EVICEL®) or an onlay dural patch.

If watertight closure is achieved but the surgeon feels that an adjunct (excluding the use of fibrin sealants) is required to assure durability of closure then such treatment should be applied. This will be considered a **treatment success**.

Closure of the remaining layers of the surgical site will be performed according to the surgeon's standard of practice.

- Adverse events (from time of randomization) will be collected
- Concomitant medications will be collected

7.1.4 5 Day Visit (± 2 days)

Within 5 days (± 2 days) post surgery, the following procedures will be performed and data will be recorded:

- Physical examination
- Laboratory tests: electrolytes, creatinine, full blood count (FBC), and liver function test (LFT).
- Surgical site assessment: infections will be evaluated according to the criteria listed in Appendix 1.

- Wound healing assessment & Incidence of CSF leakage
- Changes in concomitant medications.
- Date of hospital discharge (if not known at visit, captured when known)
- Adverse events.

7.1.5 30 Day Follow-Up Visit (± 3 days)

The following information will be recorded at the follow-up visit within 30 days following surgery:

- Physical examination
- Surgical site assessment: infections will be evaluated according to the criteria listed in Appendix 1.
- Wound healing assessment & Incidence of CSF leakage
- Changes in concomitant medications
- Adverse events.

7.2 Procedures for Handling Biological Samples

7.2.1 Laboratory Tests

All laboratory investigations will be performed at each local hospital laboratory. The volume of blood to be taken will be determined according to the standard practices of each hospital. The normal reference ranges and laboratory accreditation certificates must be provided to ETHICON.

7.2.2 Premature Withdrawal of Subjects for the Study

Every enrolled subject should be encouraged to remain in the study until they have completed the follow-up visit. Subjects may discontinue participating in the study at any time and for any reason. However, if the subject decides to discontinue participating in the study, the reason must be documented when possible. Reasons for early withdrawal include, but are not limited to:

- Consent withdrawn by the subject;
- Subject refusal to complete study visits and/or procedures;
- Lost to follow-up: a certified letter will be sent to the subject at their last known address, after a minimum of three attempts to reach the subject by telephone have failed. If communication via certified letter is unsuccessful, the subject will be considered lost to follow-up.

Subjects who discontinue from the study prematurely will not be replaced.

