Paediatric subjects for this study are classified as:

- Newborn infants (birth to 27 days. Pre-term newborn infants born \leq 37 weeks gestation will be included within the group)
- Infants and toddlers (28 days to <24 months)
- Children (2 to 11 years)
- Adolescents (12 to <18 years)

42 paediatric subjects with intra-operative cerebrospinal fluid (CSF) leak following primary suturing of the dura will be randomized in a 2:1 allocation ratio and will be stratified by surgical procedure, posterior fossa or supratentorial to either EVICEL® Fibrin Sealant (Human) or additional dural sutures.

Subjects will be followed post-operatively through discharge and for 30 days (\pm 3 days) post-surgery. The incidence of CSF leaks will be assessed within 5 days (\pm 2 days) and 30 days (\pm 3 days) post-operatively as detected by any of the following: clinical observation, diagnostic testing or the need for surgical intervention to treat a CSF leak or pseudomeningocele.

SUBJECTS RANDOMIZED TO EVICEL®

For subjects randomized to receive EVICEL® Fibrin Sealant (Human), a thin layer will be applied to the entire length of the suture line and the adjacent area to at least 5mm away, including all suture holes. If necessary, a second layer of EVICEL® may be applied. A cure time 1-2 minutes should be allotted between layers to allow for polymerization. CSF leakage will be evaluated with a Valsalva maneuver 20-25 cm H₂O for 5-10 seconds.

If CSF leakage is still apparent a second treatment (up to two layers) with EVICEL® may be applied. CSF leakage will be re-evaluated with a second Valsalva maneuver 20-25 cm H₂O for 5-10 seconds.

- If watertight closure is not evident after this final Valsalva maneuver, the subject will be deemed a failure and the surgeon may revert to his/her standard of care for closure including the use of other commercially available fibrin sealants (except EVICEL®) or an onlay dural patch.
- If watertight closure is achieved, no further treatment, including the use of onlays, will be allowed.

Closure of the remaining layers of the surgical site will be performed according to the surgeon's standard of practice.

SUBJECTS RANDOMIZED TO CONTROL

Subjects randomized to Control (Additional Sutures) will receive additional dural repair sutures applied immediately to the dural suture line after randomization as deemed necessary by the surgeon. CSF leakage will be evaluated with the Valsalva maneuver 20-25 cm H₂O for 5-10 seconds.

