3. OVERVIEW OF STUDY DESIGN

This is a prospective, randomized, open-label, multi-center controlled study evaluating the safety and effectiveness of EVICEL® as an adjunct to sutured dural closure compared to standard adjunctive dural closure techniques using additional repair sutures only to obtain an intraoperative watertight dural closure. Subjects will be screened and selected from the patient population of approximately 4-8 clinical sites.

Subjects will undergo an elective or urgent posterior fossa or supratentorial procedure (craniectomy or craniotomy). Upon completion of the primary sutured dural repair, the closure will be evaluated for intraoperative CSF leakage with a baseline Valsalva maneuver 20-25 cm H₂O for 5-10 seconds. If a spontaneous leak is apparent immediately after dural closure, no Valsalva will be performed. Subjects who have an identified CSF leak (spontaneous or as identified with the Valsalva) will be enrolled into the study.

Subjects will be randomized to either EVICEL® Fibrin Sealant (Human) or to adjunctive dural closure techniques using Additional Sutures only (Control) in a 2:1 allocation ratio and will be stratified by surgical procedure, posterior fossa or supratentorial.

Subjects will be followed post-operatively through discharge and for 30 days (± 3) post-surgery. The incidence of CSF leaks will be assessed within 5 days (± 2 days) and 30 days (± 3 days) post-operatively as detected by any of the following: clinical observation, diagnostic testing or the need for surgical intervention to treat a CSF leak or pseudomeningocele.

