11. REGULATORY OBLIGATIONS

11.1 Informed Consent

Prior to participation, the study procedures and any known or likely risks will be explained to the subjects (as applicable) and/or their parent or legal guardian by the investigator or other qualified study personnel. An Informed Consent Form and patient information leaflet, as applicable, will also be provided containing all the required information. Any questions will be answered and the patient and/or their parent or legal guardian will then be given sufficient time to consider their participation in the study before signing a consent form. For paediatric subjects who possess the intellectual and emotional ability to comprehend the concepts involved in the trial, must also give their assent to participate in the study. An age appropriate patient leaflet/assent will be provided. Subjects and/or their parent or legal guardian should receive a copy of the Informed Consent Form.

The Investigator (or designee) will explain that the subjects and/or parent or legal guardian are completely free to refuse to enter the study or to withdraw from it at any time, without any consequences for their further care and without the need to justify.

Each subject and/or their parent or legal guardian will be informed that the subject's source medical records may be checked by representatives from the Sponsor or from a regulatory agency, in accordance with applicable regulations. However, they should be made aware that all information will be treated with confidentiality, and a study ID code or number will identify them.

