8.2 Primary effectiveness analysis

The primary effectiveness endpoint is the proportion of success (intraoperative watertight closure) in the treatment of intraoperative CSF leakage defined as no CSF leakage from dural repair intraoperatively, during a Valsalva maneuver 20-25 cm H₂O for 5-10 seconds.

No formal sample size calculation has been performed for this study. The sample size required for the trial is 42 randomized paediatrics subjects recruited from 6-8 sites within the European Union. This sample size is considered adequate by EMA Paediatric Investigation Plan to summarize the data descriptively.

The primary effectiveness endpoint will be analyzed using the FAS and the PP set. However, the primary analysis will be based on the FAS. The PP analysis will be considered confirmatory.

In all cases, treatment allocation will be based on randomization for the primary effectiveness endpoint using the FAS. If more than two subjects are mis-randomized, then an additional confirmatory analysis based on treatment received will be performed for the primary effectiveness endpoint, using the FAS.

The proportion of successes will be summarized descriptively by treatment group. In addition, a two-sided 95% confidence intervals (CIs) will be reported for the ratio of the proportion of success in the EVICEL group/proportion of success in Control group (P_E/P_C), using the Farrington-Manning score method.

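### When a family refuses a follow-up visit but consent stands, the plan does not provide for collecting leak and infection status, and the Protocol then counts the gap as a failure

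*Protocol*

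**What the plan says.** - **Withdrawal.** Protocol 7.2.2 asks that "Every enrolled subject should be encouraged to remain in the study until they have completed the follow-up visit". Its list of reasons for leaving early has "Consent withdrawn by the subject" and, as a separate item, "Subject refusal to complete study visits and/or procedures". It adds that "Subjects who discontinue from the study prematurely will not be replaced". It does not say what is collected afterwards.
- **Capture.** Protocol 7.1.5 records the day-30 information at the follow-up visit. Protocol 9.7 collects adverse events through the admission and up to completion of that visit. Neither says what happens if the visit is refused.
- **How a leak is established.** Protocol section 3 accepts "clinical observation, diagnostic testing or the need for surgical intervention to treat a CSF leak or pseudomeningocele", and SAP sections 2 and 3 use the same definition.
- **Records.** Protocol 11.1 tells families that "the subject's source medical records may be checked by representatives from the Sponsor".
- **Analysis set.** Protocol 8.4.1 and SAP section 9 summarise leak and SSI on the Safety Set, defined in Protocol 8.2.1 as all treated subjects.
- **Missing data.** Protocol 8.5 treats missing secondary endpoints as failures. SAP 8.5.1 sets an outcome rule for the primary endpoint only, apart from rules for partial dates. SAP section 4 declares no changes to the planned analysis.

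**The concern.** The randomised treatment and the primary endpoint are both complete in theatre. Withdrawal after surgery can therefore affect only follow-up: leak, SSI, adverse events and laboratory tests. Declining to travel for a visit is different from withdrawing permission to use data, but 7.2.2 puts the two in one list without saying what each means for data collection. Each of the 4 to 8 sites is left to decide, in an open-label trial.

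Most of what the leak definition relies on would normally leave a trace in the hospital record, so some of these missing values are avoidable. The rule for filling them makes this matter more. Under Protocol 8.5 a missing day-30 outcome becomes a failure, and for a leak or infection endpoint the natural meaning of failure is that the event occurred. A well child whose family skips the visit could then appear in the safety table as a leak or an SSI. Under the SAP the same child has no defined handling.

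**Working it through.** **Inputs.** Total and ratio come from the Protocol synopsis: "42 paediatric subjects with intra-operative cerebrospinal fluid (CSF) leak following primary suturing of the dura will be randomized in a 2:1 allocation ratio". There is no power calculation to reproduce (SAP 8.2: "No formal sample size calculation has been performed for this study"). The documents give no loss rate, so 0 to 3 children per arm with missing day-30 status is assumed.

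**Arm sizes.** 42 × 2/3 = 28 EVICEL; 42 × 1/3 = 14 Control.

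**Weight of one child.** 1/28 = 3.6 points; 1/14 = 7.1 points.

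**No true leak, m children missing.** Observed cases give 0/(N − m). The Protocol 8.5 rule, reading failure as a leak, gives m/N. Intervals are exact (Clopper-Pearson) two-sided 95%.

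| Arm | m | Observed cases (upper limit) | Missing as failure (95% CI) |
|---|---|---|---|
| EVICEL | 0 | 0/28 (12.3%) | 0/28 = 0% (0 to 12.3%) |
| EVICEL | 1 | 0/27 (12.8%) | 1/28 = 3.6% (0.1 to 18.3%) |
| EVICEL | 2 | 0/26 (13.2%) | 2/28 = 7.1% (0.9 to 23.5%) |
| EVICEL | 3 | 0/25 (13.7%) | 3/28 = 10.7% (2.3 to 28.2%) |
| Control | 0 | 0/14 (23.2%) | 0/14 = 0% (0 to 23.2%) |
| Control | 1 | 0/13 (24.7%) | 1/14 = 7.1% (0.2 to 33.9%) |
| Control | 2 | 0/12 (26.5%) | 2/14 = 14.3% (1.8 to 42.8%) |
| Control | 3 | 0/11 (28.5%) | 3/14 = 21.4% (4.7 to 50.8%) |

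**One observed Control leak, two Controls missing.** The true rate lies between 1/14 = 7.1% and 3/14 = 21.4%. Observed cases give 1/12 = 8.3%; the Protocol rule gives 21.4%.

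**Effect on the comparison.** Two missing in each arm with no true leak gives 7.1% against 14.3%, a difference made only by arm size. Equal loss rates (2/28 and 1/14) shift both arms by 7.1 points: the comparison is spared, but the level is not.

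**Precision.** The chance of seeing at least one Control leak is 1 − (1 − p)^n. At an assumed p = 5% it falls from 51.2% (n = 14) to 46.0% (n = 12); at 10%, from 77.1% to 71.8%. The loss of information is small; the shift from imputation is much larger.

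**If status were recovered for every child.** The denominators stay at 28 and 14. With no leak found, the upper limits are 12.3% and 23.2%, as in the m = 0 rows.

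**The case against.** A reader might infer three stronger things from 7.2.2, and the documents support none of them.

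- *That collection stops after a refusal and recorded outcomes are discarded.* The text neither stops collection nor continues it. Other routes exist: adverse events are collected throughout the admission (Protocol 9.7) and include leaks and pseudomeningocele (8.4.1); serious events are reportable within 24 hours of awareness (9.8); SAP 8.4 tabulates re-hospitalisations and procedures since the previous visit; and 7.2.2 requires at least three telephone attempts and a certified letter before a child counts as lost. None of these clearly covers a child classed as withdrawn.
- *That declining one blood sample triggers withdrawal.* The list gives reasons to document once a subject has chosen to discontinue. It is not a trigger, although its wording is broad enough to be applied that way.
- *That such children drop out of the denominators.* Under Protocol 8.5 and the Safety Set they stay in and count as failures.

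Other points also stand. Non-replacement is not a flaw, since a replacement would not recover the missing outcome. The records sentence in Protocol 11.1 covers checking by the sponsor or a regulator, not collecting outcomes after a subject leaves. That non-attendance differs by arm is plausible without blinding but not documented. The secondary endpoints are descriptive only (SAP 9.4). A site's own record may miss events treated elsewhere.

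The gap survives all of this: no text provides for day-30 status when a visit is refused and consent stands, and the two documents differ on what a missing value then means.

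**Conclusion.** The point holds as a gap in the plan and a cheap improvement; it does not threaten the main result. The primary endpoint is measured in theatre, so withdrawal after surgery cannot affect it. What is exposed is the descriptive leak and SSI table, where each missing child can add 3.6 points (EVICEL) or 7.1 points (Control) to the reported incidence, and two missing Controls with no true leak give 14.3%.

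This rests on three assumptions: the derived 28:14 split, an assumed number missing per arm, and reading failure in Protocol 8.5 as occurrence of the leak or infection, which the Protocol does not spell out. If no child misses the visits, nothing changes.

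**What to change.** 1. **Protocol 7.2.2.** Replace the refusal item with text such as: *Refusal of a visit or procedure is a missed assessment, not withdrawal. Unless consent for further data is withdrawn, the site records CSF leak, pseudomeningocele, SSI, reoperation, readmission and SAEs through day 30 from the hospital record or a telephone call, flagged as record-based.* Apply the same to children lost to follow-up, as far as the record allows.
2. **Consent form.** Add a matching sentence, because the present wording covers only the checking of records.
3. **Protocol 8.5 and SAP 8.5.1.** Reconcile them for the secondary endpoints and state what failure means for leak and SSI.
4. **Reporting.** Beside any missing-as-failure result, give the observed-case result and the number imputed in each arm.

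The cost is one protocol paragraph, one consent sentence, a flag on the day-30 CRF page, and a short SAP edit with extra table rows. The downside is that record-based outcomes are less complete than an examination and may miss events treated elsewhere, which is why they are flagged.
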